## **4 Study subjects**

### **4.1 Subject accountability**

The number of subjects who were screened, who were randomized, who were dosed, and who completed treatment, along with reasons for discontinuing treatment and withdrawing from the study, will be presented by treatment group and overall. In certain cases, CRF text detailing the reasons for discontinuation and/or withdrawal may suggest additional clarification of the reason provided on the CRF. Therefore, additional information for subject accounting may be presented, utilizing reasons for discontinuing treatment and/or withdrawing from the study reclassified based on the detailed CRF text, prior to database lock. Listings of those subjects who discontinued treatment and/or withdrew from the study and the reasons for discontinuation/withdrawal will be presented.

### **4.2 Demographic and baseline disease characteristics**

Baseline data (demography, medical history, SMA history, baseline disease characteristics, baseline quality of life) will be summarized.

Demography includes age, sex, ethnicity and race. Medical history will be coded in MedDRA and the number and percentage of subjects with each history by preferred term presented, including the presence of scoliosis and presence of contractures. SMA history includes age of symptom onset, time from disease onset to enrollment, age at SMA diagnosis, time from diagnosis to enrollment, number of copies of the SMN2 gene, highest motor function achieved, current motor function, wheelchair use, and amount of physical therapy.

Baseline disease characteristics will be assessed by weight, height, ulnar length, weight for age, height for age, HFMSE, motor milestones, Upper Limb Module Test. These assessments are further described in the next paragraph and Section 5.

Weight for age and height for age will be summarized using the WHO child growth standards (WHO Child Growth Standards, 2006) for subjects aged up to 5 years and similarly the WHO growth reference data (WHO, 2007) for older subjects. These standards comprise percentiles for weight and height for age by sex and are available on a website ([www.who.int](http://www.who.int)) in txt files. Subjects will be cross referenced with these files, given the age and sex of the subject to determine below which percentile they lie for each parameter. The frequency and percentage will then be summarized for each of weight for age and height for age in the following categories:  $\leq 1^{\text{st}}$ ,  $\leq 3^{\text{rd}}$ ,  $\leq 5^{\text{th}}$ ,  $\leq 15^{\text{th}}$ ,  $\leq 25^{\text{th}}$ ,  $\leq 50^{\text{th}}$  and  $> 50^{\text{th}}$  percentile. The standards do not provide weight for age percentiles for subjects aged  $> 10$  years since this is not an appropriate measure due to the confounding effect of the pubertal growth spurt. Therefore, subjects aged  $> 10$  years at baseline will not be included in the summary for this parameter.

Baseline quality of life and caregiver burden of SMA will be assessed by PedsQL and ACEND, respectively.

Demographic, baseline disease characteristics, and baseline quality of life will be presented for the ITT Set, PPS and the Safety Set as appropriate.

Formal statistical analyses will not be done to test for homogeneity between treatment groups. If there are apparent heterogeneities between the groups in any of the subject characteristics that are of clinical importance or could affect the treatment outcome, the impact of the imbalances will be investigated and, if appropriate, adjustments made in the efficacy and safety analyses.

#### **4.3 Extent of exposure**

The number of doses received and the number of sham procedures performed will be displayed using frequency distributions. The amount of ISIS 396443 administered will be presented using summary statistics.

Overall time on study will be defined as the total number of days a subject is known to be followed on study calculated as follows:

Overall time on study =

(Last date on study) – (Date of first dose or first sham procedure) + 1.

The last date on study is defined as the latest visit or telephone contact or evaluation date or time of death from all available data for a given subject.

Time on study will be categorized into the following intervals: 0 to  $\leq 90$ , 91 to  $\leq 180$ , 181 to  $\leq 270$ , 271 to  $\leq 360$ , 361 to  $\leq 450$ ,  $> 450$  days and summarized by treatment group and overall.

Given the long half-life of ISIS 396443, subjects are considered to be exposed to study drug from the time the first dose was administered to the last day of follow-up. Essentially, exposure is equivalent to time on study.

#### 4.4 Concomitant therapy

Throughout the study concomitant medications or treatments deemed necessary for treatment of adverse events or to provide adequate supportive care may be prescribed. A concomitant medication is any non-protocol specified drug or substance including over-the-counter medications, herbal medications and vitamin supplements. Subjects are prohibited from receiving other experimental agents during the study including marketed agents at experimental doses that are being used for the treatment of SMA (e.g., oral albuterol/salbutamol, riluzole, carnitine, creatine, sodium phenylbutyrate, valproate, hydroxyurea). All concomitant medications will be coded using the World Health Organization drug dictionary (WHODrug).

A concomitant procedure is any therapeutic intervention (e.g., surgery/biopsy) or diagnostic assessment (e.g., X-ray) performed between screening and last visit. All ancillary procedures will be coded using MedDRA.

For the purposes of analysis, a concomitant therapy (including medication or ancillary procedure) is defined as any therapy that was taken on or after the first injection of ISIS 396443 or first sham procedure. This includes therapies that were started prior to the initiation of dosing/sham procedure if their use continued on or after the date of the first injection/first sham procedure. In order to define concomitant therapies with missing start or stop dates, the following additional criteria will be used:

- if both the start and stop dates of a particular therapy were missing, that therapy is considered concomitant;
- if the start date of a therapy was missing and the stop date of that therapy fell on or after the date of dosing, that therapy is considered concomitant;
- if the start date of a therapy was prior to the date of dosing and the stop date of that therapy was missing and the therapy was listed as continuing, that therapy is considered concomitant;
- if the start date of a therapy was prior to the date of dosing and the stop date of that therapy was missing and the therapy was listed as *not* continuing, that therapy is considered concomitant; or
- if the start/stop date of a therapy is partial then where it is not possible to rule out that it was not taken concomitantly it will be considered concomitant.

Denote the end date of medication as CMENDT and the study treatment/sham procedure start date as TRTSTDT. The medication is classified concomitant provided any of the following is NOT true:

- CMENDT is complete and CMENDT is less than TRTSTDT.
- Day of CMENDT missing and year/month of CMENDT is strictly before year-month of TRTSTDT.
- Month of CMENDT is missing and year of CMENDT is strictly before year of TRTSTDT.

The number and percentage of subjects taking each type of concomitant medication at baseline and during the study will be presented by preferred name for Safety Set. The number and percentage of subjects who underwent each type of ancillary procedure during the study will be presented.

Medications taken as part of the sham or lumbar puncture procedure are collected in the unblinded CRF and these will be presented separately.

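### The end-date rule in SAP 4.4 for concomitant medications, read literally, flags every recorded medication, including those stopped before the first dose or sham

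*SAP*

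**What the plan says.** SAP 4.4 states the classification twice, first in prose and then as an algorithm.

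In prose, a concomitant therapy is, for analysis, "defined as any therapy that was taken on or after the first injection of ISIS 396443 or first sham procedure". A therapy begun earlier counts only if its use carried on to that date or beyond. Five bullets then deal with missing or partial dates. The second, for a missing start date, requires that "the stop date of that therapy fell on or after the date of dosing". The fifth, for partial dates, says that "where it is not possible to rule out that it was not taken concomitantly it will be considered concomitant".

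The algorithm writes CMENDT for the medication end date and TRTSTDT for the first dose or sham date. It reads: "The medication is classified concomitant provided any of the following is NOT true". The conditions are:

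1. "CMENDT is complete and CMENDT is less than TRTSTDT"
2. "Day of CMENDT missing and year/month of CMENDT is strictly before year-month of TRTSTDT"
3. "Month of CMENDT is missing and year of CMENDT is strictly before year of TRTSTDT"

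The table concerned, which gives counts and percentages drug by drug, is described thus: "concomitant medication at baseline and during the study will be presented by preferred name for Safety Set". SAP 1.2 lists concomitant medication use among the safety and tolerability endpoints.

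**The concern.** Each condition is one way of establishing that a medication ended before treatment. The natural rule is that a medication is concomitant unless one of them holds. The sentence as written says something else: it is enough that at least one condition fails. Because the conditions need different states of the end date, at least one always fails and the rule excludes nothing.

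That conflicts with the prose definition in the same section and leaves the missing-date bullets with no work to do. The algorithm is the only part of 4.4 expressed in variable names, so a programmer could reasonably code from it. If it were coded literally, medications taken only before treatment would carry the concomitant flag and could be tabulated as use during the study.

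**Working it through.** The plan gives no figure to reproduce. The question is one of logic, so the check is a truth table followed by an enumeration.

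**Inputs.** Call the three SAP 4.4 conditions A, B and C.

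- A: year, month and day are all present, and the date is before TRTSTDT.
- B: the day is missing, and the year-month is before that of TRTSTDT.
- C: the month is missing, and the year is before that of TRTSTDT.

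**Rules compared.**

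- Literal: concomitant = (not A) or (not B) or (not C), which equals not (A and B and C).
- Corrected: concomitant = (not A) and (not B) and (not C).

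A requires a complete date, while B and C require an incomplete one, so A and B and C is impossible and the literal rule is always satisfied. If B is also allowed to apply when the month is missing, two conditions can be true together, but never three.

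**Truth table**, with an assumed first dose on 15 June 2015:

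| End date | A | B | C | Literal | Corrected |
|---|---|---|---|---|---|
| 14 Jun 2015 | T | F | F | concomitant | not |
| 15 or 16 Jun 2015 | F | F | F | concomitant | concomitant |
| May 2015, day missing | F | T | F | concomitant | not |
| Jun 2015, day missing | F | F | F | concomitant | concomitant |
| 2014, month and day missing | F | F | T | concomitant | not |
| 2015, month and day missing | F | F | F | concomitant | concomitant |
| Entirely missing | F | F | F | concomitant | concomitant |

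**Enumeration.** 1,557 end-date patterns around the same date were classified: 1,500 complete, 48 with only the day missing, 8 with the month missing and 1 entirely missing.

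- The most conditions true for any one record was 1.
- The literal rule flags 1,557 of 1,557. That includes all 895 with a complete end date before first dose, and all 928 that provably ended before it.
- The corrected rule flags 1,557 − 928 = 629, including 0 of the 895. It disagrees with the prose definition (concomitant unless the end date proves an earlier stop) in 0 cases.

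The choice of first-dose date does not matter, because the incompatibility lies in the conditions themselves.

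**Which records could be affected.** Protocol 8.11.1 counts therapies from the start of screening, and SAP 2.1 limits screening to 28 days before the first dose or sham. If recording follows that window, the excess is mainly drugs stopped within those 28 days. A complete end date on any of the 28 is flagged by the literal rule, and on none by the corrected rule.

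**Scale for one table row**, using the group sizes in SAP 5.1 (126 in all, 84 and 42):

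- One child: 1/126 = 0.8%, 1/84 = 1.2%, 1/42 = 2.4%.
- Assumed range of 1 to 5 children for a given drug: 0.8% to 5/126 = 4.0% overall.

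A row changes only if the child did not also take the same drug on or after first dose.

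**The case against.** The best defence is that the section settles its own meaning. The prose definition governs, and the end-date lines restate it compactly. A rule that flags everything classifies nothing, so a careful programmer would probably see a slip and code the intended version. That is fair, and it is why this is a wording error and not a flaw in the intended analysis. It does not make the sentence correct, and a derivation rule should not need a charitable reading.

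A second point is that the fifth missing-date bullet has its own stray negative. Taken literally, it makes a therapy concomitant when *non*-use cannot be ruled out. This stands: the corrected rule matches four bullets as written, and the fifth in its evident meaning.

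Third, the effect on the table depends on its layout. The table covers baseline as well as the study period, baseline is not defined for medications, and the SAP does not say how the two are separated. If start and stop dates make the split, a drug stopped before dosing might never appear as use during the study. This also stands, so the consequence is conditional.

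Fourth, the percentages are simply one over the group size, and the 1-to-5 range has no source in the documents. Agreed; they are illustrative only.

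Finally, Protocol 8.11.1 uses a broader definition starting at screening, which the literal output would resemble. But SAP 4.4 sets its narrower definition expressly for analysis, so the contradiction within the section remains.

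**Conclusion.** The point holds. As written, the end-date rule in SAP 4.4 is always satisfied, and it contradicts the section's own analysis definition for any medication that demonstrably ended before the first dose or sham. This follows from the three conditions alone.

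The importance is low. The number of records affected cannot be derived from the documents. Any excess should be mainly drugs stopped during screening, assuming recording starts there, and it reaches the table as use during the study only if the flag is what places them in that column. The rule does not depend on treatment arm, and no between-group bias is claimed. The per-protocol exclusion for SMA medicines in SAP section 3 has its own wording and does not refer to this rule. No efficacy test, alpha level or power figure depends on it.

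**What to change.** In the sentence that introduces the three conditions in SAP 4.4, require that *none* of them is true, in place of asking that any one be untrue. This restores the section's definition: a medication whose end date proves an earlier stop is excluded, and one whose end date is missing or leaves the matter open stays concomitant.

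It would be sensible to remove the stray negative from the fifth missing-date bullet in the same edit, and to say how the table separates baseline use from use during the study.

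The necessary change is one phrase. It needs no new data and has no effect on efficacy testing.

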#### **4.5 Protocol deviations**

Protocol deviations identified during site monitoring will be captured in a protocol deviation log and categorized as major or minor deviations. These deviations will be listed. Major protocol deviations will be summarized including those that lead to exclusion from the Per-protocol Set.

## 5 Efficacy data

The primary, secondary, and tertiary efficacy endpoints are listed in Section 1.1.

### 5.1 Interim and final efficacy analyses

An interim analysis may take place when all subjects have completed the 6-month assessment and at least 39 subjects have completed the 15-month assessment with a targeted clinical cut-off date of 31 August 2016. At the interim analysis, only the primary endpoint will be tested. The final efficacy analysis will take place when the last subject completes the 15-month assessment or earlier if the study is terminated on the grounds that conducting a sham-controlled study is no longer deemed ethical based on the assessment of risk-benefit of ISIS 396443.

At the interim analysis and final analysis, the same analysis of covariance (ANCOVA) model will be used in analyzing the change from baseline in HFMSE score to month 15. At the interim analysis, the month 15 endpoint values will not be available for some patients, so a multiple imputation method will be used to estimate them ([Section 5.3](#)). This method will also be used in the final analysis for the primary endpoint

The interim analysis results will be reviewed by an independent Data Safety Monitoring Board (DSMB) and an Unblinded Senior Management Team from the Sponsor. Recommendation will be made on whether it is appropriate for the trial to continue according to the current protocol or whether the protocol needs to be modified. During the interim analysis, subjects will continue in the study.

In the protocol it had been planned to conduct the interim efficacy analysis with an alpha of 0.02, however in finalizing this statistical analysis plan it was decided to conduct the interim analysis at a significance level of 0.025. If the study is not stopped at the interim analysis, the final analysis (test and confidence interval estimate procedures) will be conducted at a significance level determined by the resampling procedure as follows.

Let  $T_1$  and  $T_2$  be the standardized test statistics at the interim and final analyses, respectively. In order to determine the alpha level for the final analysis, the correlation between  $T_1$  and  $T_2$  is first estimated based on the resampling approach (Westfall and Young 1993):

- Among the 126 subjects enrolled in the study, randomly assign 84 subjects to the ISIS 396443 group and 42 subjects to the sham control group.
- Apply the re-randomized treatment assignment to the interim data and obtain the standardized test statistics  $T_1$ .
- Apply the re-randomized treatment assignment to the final data and obtain the standardized test statistics  $T_2$ .

Repeat the above procedure  $N$  times ( $N=10000$ ) and obtain  $N$  pairs of test statistics  $T_1$  and  $T_2$ . The correlation between  $T_1$  and  $T_2$  will then be estimated as the sample correlation of the  $N$  pairs.

Let  $c_1$  be the cut-off point for the interim two-sided test corresponding to an alpha of 0.025. Once the estimated correlation  $\rho$  is available, the cut-off point  $c_2$  for the final analysis is obtained by solving the nonlinear equation  $\Pr(|T_1| \geq c_1 \text{ or } |T_2| \geq c_2) = 0.05$ , where  $(T_1, T_2)$  follow a bivariate normal distribution with mean vector  $(0, 0)$ , standard deviations of 1 and correlation  $\rho$ .

## 5.2 Statistical testing procedures

Secondary efficacy endpoints have been rank prioritized:

[figure not shown]
- the proportion of subjects who achieve a 3-point or greater increase from baseline HFMSE score at 15 months
- the proportion of subjects who achieve any new motor milestone at 15 months
- the number of motor milestones achieved per subject at 15 months
- the change from baseline in Upper Limb Module Test at 15 months
- the proportion of subjects who achieve standing alone at 15 months
- the proportion of subjects who achieve walking with assistance at 15 months.

In order to control the Type I error rate at 0.05 across interim and final analyses for the testing of primary and secondary efficacy endpoints, a stage wise hierarchical strategy utilizing independent alpha spending functions for primary and secondary endpoints (Glimm et al. 2010) will be applied. In the framework of the stage wise hierarchical testing, since the secondary endpoints will not be tested at the interim (i.e., no alpha spending), at the final analysis alpha = 0.05 will be used in the sequential testing. The entire procedure is described below.

At the interim analysis, the primary efficacy endpoint will be tested at an alpha of 0.025. If the primary efficacy endpoint is statistically significant at the interim analysis, then the secondary endpoints may be descriptively reported. No formal statistical comparison will be performed and no p-values will be calculated for statistical inference for these endpoints. The only alpha spending proposed at the interim analysis is based on analysis of the primary efficacy endpoint, the only endpoint at the interim for which formal statistical testing will be conducted.

In the event of a decision by the study Sponsor to terminate the study earlier on the grounds that conducting a sham-controlled study is no longer deemed ethical based on an updated risk-benefit assessment of ISIS 396443 from the planned interim analysis, all subjects will be invited for the EODBP study visit, during which all Day 456 assessments will be conducted. The EODBP visit should occur no less than 2 weeks from the most recent dosing/sham procedure administered. After completing the EODBP visit, subjects will be considered study completers and will be allowed to enroll into the OLE study. Under this scenario, since patient participation and monitoring continue until the study is stopped, the final analysis that incorporates the accrued data will be conducted. At the final analysis, the primary efficacy endpoint will not be tested again since significance has already been achieved at the interim. The secondary endpoints will be tested at an alpha of 0.05 as shown in the diagram below.

In a scenario where the primary efficacy endpoint is not significant at the interim analysis, no additional data will be evaluated. In this case, at the final analysis, the primary endpoint will be tested at an alpha level determined based upon the resampling approach method. If the primary endpoint is not significant at the final analysis, then the testing of the secondary endpoints will be considered exploratory. If the primary endpoint is significant at the final analysis, then the secondary endpoints will be tested at an alpha of 0.05 as shown in the diagram below.

In the event that a secondary endpoint is not significant and formal testing is ended, the remaining endpoints will be tested but the results will be considered exploratory.

Analyses of tertiary efficacy endpoints will not include adjustments for multiplicity.

The analysis of safety data for the interim analysis will include all subjects who have received at least one dose of study treatment as of the targeted clinical cut-off date.

Although statistical stopping guidelines have been pre-specified for the interim analysis, a number of factors must be considered thoroughly as part of the decision to modify or stop the study. A recommendation to modify or stop the study will, therefore, not be based solely on statistical grounds.

### 5.3 Multiple Imputation of missing data

In the protocol it was stated that the multiple imputation procedure would be used to impute missing values for all primary and secondary efficacy endpoints. However in finalizing this statistical analysis plan it was decided that to handle the missing data in the WHO motor milestones, the multiple imputation procedure won't be used because historical data showed that it's very rare for non-ambulatory SMA patients to achieve certain milestones (such as walking alone). Therefore, an imputation approach based upon multiple imputation would face challenges due to low or zero numbers of subjects in the sham arm achieving a response. The imputation rules and analyses for motor milestones are detailed in Section 5.6.2.

